### 6.1.7. Tolerability data

The overall safety profile of axitinib is similar to the profile of other drugs belonging to the same class of molecules that inhibit the VEGF pathway. However, the aforementioned greater selectivity of axitinib compared to other targeted therapies such as sorafenib gives it a better safety profile, with less toxicity caused by the off-target effect being seen with axitinib. These adverse events (AEs) include common events such as diarrhoea, nausea, high blood pressure (HBP), tiredness and dermatological events, as well as fewer common toxicities such as thromboembolic events, hypothyroidism and proteinuria. However, it should be noted that axitinib does not appear to have the same degree of elevated liver enzymes and potential for liver failure as described with certain other VEGF-pathway inhibiting molecules. In view of the above, the EMA recommends monitoring specific safety events such as heart failure, HBP, thyroid function, embolic and thrombotic events, arterial and venous events, erythrocytosis, proteinuria, etc., before starting treatment and regularly throughout treatment. In the pivotal study, the most common grade  $\geq 3$  AEs ( $\geq 10\%$ ) were HBP (17%), diarrhoea (11%) and fatigue (10%), whereas in patients receiving treatment with sorafenib palmar-plantar erythrodysesthesia and hypertension were reported in 17% and 11%, respectively. It should be pointed out that, in the axitinib arm, no deaths were reported that were related to the drug, while two deaths associated with sorafenib were reported: one case associated with retroperitoneal bleeding due to tumour necrosis and another associated with gastrointestinal bleeding, whereas the rate of withdrawals due to related AEs favoured axitinib (4% vs 8%). In the COMPARZ study, which directly compared pazopanib and sunitinib, the common toxicity profiles were reflected in: the median duration of treatment (8.0 m vs 7.6 m), number of dose reductions (44% vs 51%), and rate of discontinuation due to AEs (24% vs 19%), for pazopanib and sunitinib, respectively. By contrast, in the AXIS study, 31% of patients reduced their dose in the axitinib arm versus 52% in the sorafenib arm.

#### **6.1.8. Administration regimens**

The recommended starting dose of axitinib is 5 mg twice daily, every 12 hours, with or without food (with a glass of water), with dose increases or decreases being recommended in accordance with patient safety and tolerability. Patients who tolerate the starting dose of axitinib of 5 mg twice daily for two consecutive weeks, without presenting any serious adverse reactions, may increase the dose to 7 mg twice daily, unless the patient's blood pressure is  $>150/90$  mmHg or the patient is receiving antihypertensive treatment. Therefore, using the same criterion, patients who tolerate an axitinib dose of 7 mg twice daily may increase the dose to a maximum of 10 mg twice daily.

Control of some adverse reactions may require a temporary or permanent suspension and/or a reduction in the dose of the treatment with axitinib. When the dose reduction is necessary, the dose of axitinib may be reduced to 3 mg twice daily or even 2 mg twice daily.

Treatment should be continued as long as clinical benefit is observed, or until an unacceptable toxicity occurs that cannot be managed with concomitant medication or dose adjustment.

## 6.2. Study rationale

The efficacy and safety profile of axitinib in patients with metastatic RCC is scientifically documented in the pivotal phase III “AXIS” study, with a subgroup of patients who benefited from a longer progression-free survival, called “long-term responders” with a survival of greater than 9 months; however, due to the rigid inclusion criteria in a clinical trial, these data cannot be generalised to the population treated in normal clinical practice. Therefore, it is necessary to identify the clinical, tumour and response factors of these patients in “real” clinical practice compared to those patients with a below-average PFS.

These concepts underline the need for observational studies that respond to unresolved questions and complete the information on clinical trials, helping to improve the knowledge on the real use of drugs after they have been marketed and to confirm and reaffirm the data obtained in the development phase. So much so that, in the last few years, the European and local health authorities have started to include in their guidelines the application for real-world studies with the authorised drugs that confirm these clinical data and allow for better patient screening.

Furthermore, the studies carried out under routine clinical conditions allow us to establish whether the routine patterns used by the physician correspond with the authorisation, which is based on information obtained from clinical trials.

[REDACTED] al.

## 7. HYPOTHESIS AND OBJECTIVES

### 7.1. Primary objective:

- To describe the baseline clinical characteristics of the population of patients who are long-term responders to axitinib and to identify clinical factors associated with a long-term response to axitinib.

*For the study, “long-term responders to axitinib” has been defined as patients with progression-free survival [PFS] of at least 9 months with the drug, and “patients refractory to axitinib” has been defined as patients with disease progression in the first assessment after the start of treatment [estimated PFS  $\leq$ 3 months]*

To meet the study objective, two groups of patients with extreme response to the drug will be compared: a group of patients with long-term responses to the drug (group of long-term responders to axitinib) compared to a group of patients with disease progression in the first assessment after starting treatment (group of patients refractory to axitinib), in which the association of the following clinical factors will be analysed with the benefit of the treatment;

- Age ( $\leq$ 65 years and  $>$ 65 years)
- Baseline ECOG/PS at the start of treatment for each line (0, 1 and  $\geq$ 2)
- Number of previous treatment lines (1, 2 and  $\geq$ 3)
- Previous nephrectomy (yes and no)
- MSKCC risk group (favourable, intermediate and poor)
- IMDC risk group (favourable, intermediate and poor)
- Change in the MSKCC or the IMDC risk group with respect to the previous line (yes vs no);
- Histology (100% clear cells, main component of clear cells, main component of non-clear cells, 100% non-clear cells).

- Duration of first-line with a TKI ( $\geq 12$  months,  $\leq 6$  months;  $\leq 3$  months)
- Better response with the TKI received in first-line (CR/PR, SD, DP)
- Number of metastatic locations (1, 2 and  $\geq 3$ );
- Site of metastases (CNS metastases [yes vs no]; lymph nodes [yes vs no]; lung [yes vs no]; liver [yes vs no]; bone [yes vs no])
- Baseline LDH levels  $\leq 1.5 \times \text{ULN}$  (yes vs no)
- Baseline Hgb levels  $> \text{LLN}$  (yes vs no)
- Baseline corrected  $\text{Ca}^{++}$  levels  $\leq 10$  mg/dl (yes vs no)
- Baseline neutrophil levels  $\leq \text{ULN}$  (yes vs no)
- Baseline platelet levels  $\leq \text{ULN}$  (yes vs no)
- Neutrophil/lymphocyte ratio  $\leq 3$  (yes vs no)
- Smoking habits (smoker, non-smoker or ex-smoker)

## 7.2. Secondary objectives:

- To describe the response to treatment with axitinib in the long-term responder group (defined as a PFS of at least 9 months with the drug)
- To describe the efficacy per treatment line (second line of treatment and subsequent)
  - Best response to treatment (CR, PR, SD)
  - Progression-free Survival
  - Objective response rate (ORR) and clinical benefit (sum of CR, PR and SD)
  - Time to progression
  - Overall Survival
- To describe the duration of treatment with axitinib
- To describe the percentage of patients who titrated doses of axitinib of more than 5 mg twice daily

- To describe the percentage of patients who have reduced doses of axitinib to below 5 mg twice daily
- To describe the tolerability of axitinib
- To describe the treatments received at progression
- To describe the response to the treatments received at progression

## **8. METHODS OF INVESTIGATION**

The purpose of this study is to describe, in routine clinical practice, outside the context of a clinical trial, the clinical characteristics of patients with metastatic kidney cancer who have been treated with axitinib for at least 9 months and to identify clinical factors associated with a greater benefit from the drug. No hypotheses have been pre-specified, and all study data will be analysed using the statistical descriptive techniques.

### **8.1. Study design**

Post-authorisation, multicentre, observational study with retrospective follow-up.

In this study, the treatment with axitinib will have started before the enrolment of the patient, so the decision to treat and enrol these patients will be independent of the decision to carry out this study, and will depend exclusively on the clinical judgement of the responsible doctor.

### **8.2. Scope**

The patient population eligible for this study includes any patient with advanced or metastatic kidney cancer who has been treated with axitinib for at least 9 months or who has had PD as the best response to this treatment.

The requirements for a patient’s inclusion are that:

1. These patients must have received axitinib as second-line treatment or later, in accordance with its Summary of Product Characteristics. Two groups presenting extreme responses to the drug will be compared: one group of patients showing no evidence of disease progression for at least 9 months after the start of treatment with axitinib versus a group of patients showing disease progression while taking the drug at the first response assessment.
2. Collection of clinical, safety and response data in patients with advanced kidney cancer.

The study is expected to be conducted in at least 30 sites distributed throughout Spain in order to reach the maximum number of study patients.

The study will start at each site after the contract with the site is signed and all study documentation and information on the procedures and objectives of the study are received by the person appointed by the sponsor.

Recruitment will be competitive between all participating sites, and as many patients as there are at the site that meet the inclusion criteria during the recruitment period may be included.

This is an observational study designed to reflect routine clinical practice; there will be no interference with the daily routine medical care of patients with kidney cancer. The data collected will be consistent with those normally collected from the patient’s medical record in routine clinical practice, including the patients’ demographic data, routine laboratory values required in the diagnosis and control of this condition, performance status, clinical condition, and the assessments carried out according to the site's routine clinical practice, use of medication, tolerability, adverse events and compliance with treatment.

Given that this is an observational study, no additional material not included in routine practice will be required.

Patients will be considered assessable if they meet the inclusion criteria and do not meet the exclusion criteria, and have received at least one dose of axitinib prior to their inclusion in the study.

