### **8.2.1. Inclusion Criteria**

Patients must meet all the inclusion criteria below to be eligible for inclusion in the study:

1. *Evidence of a personally signed and dated informed consent form indicating that the patient (or his/her legal representative) has been informed of all aspects relevant to the study. Informed consent will only be obtained from patients who are still alive.*
2. *Aged 18 or over.*
3. *Histologically confirmed diagnosis of advanced kidney cancer, with at least one radiological evaluation of the disease in accordance with RECIST 1.1 criteria*

4. *Treatment with axitinib as second-line or later with a PFS equal to or greater than 9 months, or with disease progression in the first response assessment*

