#### **5.2 SUBGROUPS**

For some of the study objectives, the following two groups of patients with extreme responses to the drug are defined (see definition in point 7. Definition of variables):

- “Long-term responders to axitinib”: Patients who have a PFS of at least 9 months with the drug.
- “Patients primary refractory to axitinib”: Patients with disease progression at the first assessment after the initiation of treatment (estimated PFS  $\leq 3$  months). It means, patients with best response to axitinib=PD.

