    - Has treatment with axitinib been discontinued? (Yes/No)
      - If yes, specify:
        - End-of-treatment date
        - Reason for suspension of treatment (DP/Toxicity/Other, specify)
    - Risk criteria at discontinuation of treatment with axitinib

- 
- Time from first diagnosis to systemic treatment less than 1 year (Yes/No/Unknown)
    - ECOG/PS (current status) (Yes/No/Unknown)
    - LDH >1.5 x ULN (Yes/No/Unknown)
    - Haemoglobin < LLN (Yes/No/Unknown)
    - Corrected calcium >10 mg/dl (Yes/No/Unknown)
    - Presence of 2 or more metastatic sites (Yes/No/Unknown)
    - Platelets > ULN (Yes/No/Unknown)
    - Neutrophils > ULN (Yes/No/Unknown) (value)
  - Has there been disease progression? (No/Yes, specify date)
  - Best treatment response (CR, PR, SD, DP/Not evaluable).
    - Date of the best response obtained
  - Starting dose (5 mg/12 h; 2 mg/12 h; 3 mg/12 h; 7 mg/12 h; 10 mg/12 h)
  - Has the dose been modified? (Yes/No)
    - If yes, specify:
      - Increased/Reduced
      - Dose modification date
      - Reason for dose modification
      - New dose (5 mg/12 h; 2 mg/12 h; 3 mg/12 h; 7 mg/12 h; 10 mg/12 h; other, specify mg/h)
  - Adverse events
    - Adverse events (Anaemia; Asthenia; Fatigue; Diarrhoea; Dysphonia; Elevated ALT/GPT; Elevated AST/GOT; Elevated Bilirubin; Elevated Creatinine; Elevated Haemoglobin; Elevated Lipase; Hypercalcaemia; Hypertension; Hypocalcaemia; Hypophosphatemia; Hypothyroidism; Lymphopenia; Mucositis; Nausea; Neutropenia; Proteinuria; Rash; Hand-foot syndrome; Thrombocytopenia; Vomiting, Other, specify).
    - Worst grade according to CTCAE
    - Cycle in which the worst grade occurred
    - Related to treatment (Yes/No)
    - Serious AE? (Yes/No), if yes, specify
      - Reason (Results in death/ Is life threatening/ Leads to hospitalisation or prolongation of hospitalisation/ Causes persistent or significant disability or incapacity/ Causes a congenital anomaly or birth defect/ Is medically significant).
  - Subsequent treatments
    - Has the patient received any subsequent treatment? (Yes/No)
      - If yes, specify
        - Drug received
        - Starting dose
        - Treatment line
        - Start date

- End date
- Ongoing
- Best response attained (CR, PR, SD, DP/Not evaluable)
- Reason for discontinuation (DP/Toxicity/Other, specify)
- Vital status
  - Date of last follow-up
  - Status (Alive/Death)
    - If Death, specify
      - Date of death
      - Cause of death (DP, Other, specify)

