 $(\text{Dose increase date or Dose reduction date} - \text{Start date of treatment with axitinib}) / 30.4375$
  - Duration (months) of subsequent treatments =  
 $(\text{Date of end of subsequent treatment or of latest follow-up if not suspended} - \text{Date of start of subsequent treatment}) / 30.4375$ . In the case of several subsequent treatments per patient, proceed as follows: the duration in months of each of the subsequent treatments will be calculated (from the start date to the end date or last check if it continues). This will be done for all subsequent treatments and then proceed to make the sum per patient of all durations of subsequent treatments

- Progression-Free Survival (PFS, in months) =  
 (Date of Disease Progression on treatment with axitinib or death from any cause – Date of start of treatment with axitinib) / 30.4375  
 If there is no progression or death, the case is censored as  
 PFS (months) = (Date of latest follow-up – Date of start of treatment with axitinib) / 30.4375
- Time to progression (TTP, in months) =  
 (Date of Disease Progression – Date of start of treatment with axitinib) / 30.4375  
 If there is no progression, the case is censored as  
 TTP (months) = (Date of latest follow-up – Date of start of treatment with axitinib) / 30.4375
- Overall Survival (OS, in months) = (Date of death – Date of start of treatment with axitinib) / 30.4375  
 If death has not occurred, the case is censored as  
 Overall Survival (OS, in months) = (Date of latest follow-up – Date of start of treatment with axitinib) / 30.4375
- Overall Survival since the start of first-line treatment (OS, in months) = (Date of death – Date of start of first-line treatment) / 30.4375  
 If death has not occurred, the case is censored as  
 Overall Survival (OS, in months) = (Date of latest follow-up – Start date of first treatment) / 30.4375
- Patient subgroups
  - A-Long-term responders: comprising patients with PFS  $\geq 9$  months.
  - B-Refractory (primary): comprising patients with best response to treatment = PD. This date is collected in the CRF form “axitinib treatment”.
- MSKCC risk group (described in appendix 11.1.). It will be analysed “Before the beginning of the first line”. These calculations will be performed on patients who have data on all the variables involved (in the case of a patient who does not have data on all the variables but has > 2 factors, it will be classified in the “Poor” risk group.

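### The condition that refractory patients progress while on axitinib does not reach inclusion criterion 4 or the SAP classification rules, so some early stoppers could be classed as refractory

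*Protocol*

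**What the plan says.** The refractory group is described in several places, in different terms.

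- Protocol 8.2 (Scope), item 1 of the inclusion requirements: "a group of patients showing disease progression while taking the drug at the first response assessment". The Study population text in SAP 2.1 repeats it.
- Protocol 8.2, opening sentence: the eligible population includes anyone "who has had PD as the best response to this treatment". No on-drug condition.
- Protocol 7.1 (Primary objective): "patients with disease progression in the first assessment after the start of treatment", with an estimated PFS of 3 months or less. No on-drug condition.
- Protocol 8.2.1, criterion 4: a PFS of 9 months or more, "or with disease progression in the first response assessment". The SAP's IC4 is worded in the same way. Neither mentions best response or being on drug.
- SAP 2.1 (Analysis population), check of IC4: PD is entered as best response on the axitinib form.
- SAP 5.2: "It means, patients with best response to axitinib=PD".
- SAP 7: "B-Refractory (primary): comprising patients with best response to treatment = PD".
- SAP 7.1: a refractory patient is again one whose best response is progression. The same section says that classification rests on PFS, as given in 5.2.

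The only exposure condition is one dose of axitinib (protocol 8.2, SAP 5.1). The CRF (SAP 6) collects the axitinib end date, the progression date and the reason for stopping: "Reason for suspension of treatment (DP/Toxicity/Other, specify". No classification rule uses these three fields for the refractory group.

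**The concern.** A membership condition for one arm of the primary comparison is stated in both documents but never applied. The SAP treats item 1 of the inclusion requirements as something to verify: it checks from CRF data that axitinib was second line or later, but has no check for the on-drug half of the same item. It also says that CRF information overrides the site's yes/no eligibility answers, so the programmed check decides.

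The refractory arm is the smaller one. Patients who were intolerant or barely exposed, mixed in with patients whose tumour progressed on the drug, would dilute real differences between the groups. ECOG and comorbidities are among the factors tested against group, and baseline factors with P<0.15 go forward to the logistic model without multiplicity adjustment. If such factors predict early stopping, they could also bias the comparison, but nothing in the documents allows the size of that to be estimated.

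**Working it through.** The plan has no figure to reproduce: the sample size is an expectation, and both documents say that a calculation does not apply. The check is a comparison of the definitions and an illustration of size.

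**Definitions**

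| Place | On-drug condition? | Criterion |
|---|---|---|
| Protocol 8.2 item 1; SAP 2.1 Study population | Yes | Progression at first assessment |
| Protocol 8.2 opening; SAP 2.1 Study population opening | No | Best response = PD |
| Protocol 7.1 | No | Progression at first assessment |
| IC4 (protocol 8.2.1, SAP 2.1) | No | Progression at first assessment |
| SAP check of IC4; SAP 5.2, 7, 7.1 | No | Best response = PD |

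The reference to PFS in SAP 7.1 does not close the gap. The PFS event in SAP 7 is progression on axitinib treatment or death, but 7.1 points back to 5.2, and 5.2 resolves to best response = PD.

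**Group sizes.** About 60 patients (protocol 8.5) at about 2:1 (protocol abstract): 40 long-term responders and 20 refractory.

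**Share of the refractory group that progressed off drug**

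c = f·q / [f·q + (1−f)·P]

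- f, the proportion of treated patients stopping before the first scan for a reason other than progression: assumed 2–10%. The nearest figure in the documents is 4% withdrawal for related AEs at any time in the pivotal trial (protocol 6.1.7).
- q, the proportion of these with PD recorded at that scan: assumed 30–60%.
- P, true PD by 3 months, assuming exponential PFS with the medians in protocol 6.1.6. For 6.7 months, 1 − exp(−ln2·3/6.7) = 0.267; for 4.8 months, 1 − exp(−ln2·3/4.8) = 0.352.

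| f | q | P | c | Of 20 |
|---|---|---|---|---|
| 0.02 | 0.30 | 0.352 | 0.006/(0.006+0.345) = 0.017 | 0.3 |
| 0.04 | 0.45 | 0.352 | 0.018/(0.018+0.338) = 0.051 | 1.0 |
| 0.04 | 0.45 | 0.267 | 0.018/(0.018+0.256) = 0.066 | 1.3 |
| 0.10 | 0.60 | 0.267 | 0.060/(0.060+0.240) = 0.200 | 4.0 |

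**Effect on an odds ratio.** Assume that a factor is present in 30% of long-term responders, 60% of true refractory patients and 30% of off-drug progressors. The observed refractory prevalence is p = 0.60(1−c) + 0.30c, and OR = [p/(1−p)]/(0.30/0.70). Power is for a two-sided 0.05 comparison of two proportions.

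| c | p | OR | Power, patients kept | Power, patients left out (OR 3.50) |
|---|---|---|---|---|
| 0 | 0.600 | 3.50 | 0.61 | 0.61 |
| 0.04 | 0.588 | 3.33 | 0.58 | 0.60 |
| 0.10 | 0.570 | 3.09 | 0.53 | 0.58 |
| 0.20 | 0.540 | 2.74 | 0.44 | 0.55 |

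At c = 0.05, p = 0.585 and OR = 3.29.

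**Sampling error for comparison.** With 12/20 against 12/40, the SE of the log odds ratio is √(1/12+1/8+1/12+1/28) = 0.572. The 95% interval around 3.5 is exp(1.253 ± 1.121), about 1.1 to 10.7.

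**The case against.** The strongest reply is that the protocol never sets one clear on-drug rule. The opening of section 8.2 accepts best response = PD, section 7.1 has no on-drug wording, and section 8.3 leaves operational definitions to the SAP. On this view the SAP chose one of two wordings that the protocol already held. That stands: this is an inconsistency to reconcile. A reader might infer that the SAP dropped a settled protocol requirement; the documents do not support that.

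A reader might also infer that inclusion criterion 4 itself uses best response = PD. It does not; only the SAP's check of it does. Nor is it certain that early stoppers are counted as refractory. The field records best response to axitinib and offers a not-evaluable option, and no rule says how a first scan after stopping is to be entered. They could be counted, depending on each site's practice.

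The size is also open to challenge. The 4% covers withdrawals for related AEs at any time, so the share before the first scan for that reason cannot exceed it in that trial. The 10% ceiling and the 30–60% range have no source. With f = 2%, q = 45% and P = 31%, c is 0.009/(0.009+0.304) = 0.029, or 0.6 of 20. A shift from 3.5 to 3.3 is small against an interval of 1.1 to 10.7. This stands as to size. It does not remove the mismatch, because sampling error does not make the group definition clear.

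Last, SAP 8 imputes incomplete dates to the 15th of the month or to 15 June, so a rule on dates alone could reverse the order of events a few weeks apart. That stands and shapes the fix.

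**Conclusion.** The point holds as a gap between stated and programmed definitions. The on-drug condition in protocol 8.2 item 1 and the SAP study population text is absent from inclusion criterion 4 and from every SAP rule that assigns patients to the refractory group. Some patients who stopped early and progressed off drug could enter that arm.

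The likely size is modest: about 1 of 20 patients, with an odds ratio of about 3.3 in place of 3.5. The extreme of 4 patients and 2.7 needs the assumed inputs at their most unfavourable together. All of this rests on assumed stopping and progression rates, exponential PFS and an assumed factor prevalence. A claim that ECOG or comorbidity would emerge as false predictors goes further than the documents allow; it is a possible direction of bias only. The study is exploratory, and the evidence supports a listing and a with/without analysis better than outright removal from an arm of about 20.

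**What to change.** 1. Reconcile protocol 7.1, 8.2 (opening sentence and item 1) and 8.2.1 criterion 4 with SAP 2.1 (study population, IC4 and its check), 5.2, 7 and 7.1 on whether progression must occur on axitinib. If the sponsor prefers best response = PD alone, say so and keep steps 3 and 4.
2. In SAP 5.2 and 7, derive an on-drug flag from collected fields: reason for suspension = DP, or progression date not later than the axitinib end date. Where either date is imputed under SAP 8, let the stop reason decide.
3. List patients with best response = PD who stopped axitinib earlier for toxicity or another reason.
4. Run the primary two-group comparison and the logistic model with and without these patients.

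No new data are needed. The cost is SAP wording, one derived variable, one listing and a second run of the primary analyses. The analysis without these patients may lose one or two from the refractory arm. In the illustration, at 10% contamination (2 of 20), power is 0.58 with them left out and 0.53 with them kept.
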